SUSAR	Suspected Unexpected Serious Adverse Reaction
CNORIS	Clinical Negligence and Other Risks Scheme
SmPC	Summary of Product Characteristics
NRES	National Research Ethics Service
REC	Research Ethics Committee
MHRA	Medicines and Healthcare Products Regulatory Agency

SUMMARY

Electronic cigarettes (EC) are gaining popularity as an alternative to Traditional Cigarettes (TC). Despite not containing all the harmful substances seen in TC, EC are known to contain impurities that may have a detrimental impact on human health. The effects of ECs compared with TC on vascular function, inflammation and oxidative stress are unknown. It is increasingly recognised that nicotine itself has significant atherothrombotic effects. Therefore, clinicians are unable to confidently recommend ECs as a less risky alternative to TC.

Hypothesis: Endothelial function will be improved on EC compared to TC when measured by flow mediated dilatation (FMD).

Aims: To assess the effects of EC-nicotine and EC-nicotine free on endothelial function as compared to TC.

Design: Single centre, 2-cohort parallel group, randomised controlled trial. with a comparator TC arm

Population: ≥ 18 years old, current TC smokers. Excluding those with cardiovascular disease (hypertension allowed).

Interventions: 2 groups will be randomised to either EC-nicotine or EC-nicotine free for 4 weeks. 1 group of TC smokers will be recruited as a comparator arm

Outcomes: the primary outcome is the change in endothelial stiffness as measured by Flow Medicated Dilatation between the TC and EC-nicotine free groups. Secondary outcomes are change in endothelial stiffness between EC-nicotine free and EC-nicotine groups and change in oxidative stress between all 3 groups.

Assessments: performed at baseline and 4 weeks.

Samples size: 135 participants randomised to 2 groups EC-nicotine (n=45) and EC-nicotine free (n=45) plus a comparator arm of TC (n=45), will have a 80% power to detect an improvement in FMD of 2.0% and 1.0% in the EC-nicotine free and EC-nicotine groups respectively compared to the TC group at 5% significance. This allows for a 10%, 15%, and 20% drop-out rates in the TC, EC-nicotine & EC-nicotine-free groups respectively.

Statistical Analysis: Change in outcome measures between interventions will be assessed by a linear contrast test, and a linear regression including the baseline FMD level and experimental group as covariates.

Potential benefit: This study will provide further information on the potential use these devices and the risks and/or benefits associated with them, specifically in relation to vascular health.

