While EC are sold on the premise that they are a much cleaner alternative to TC in that they do not contain harmful substances like tobacco and tar, they do nevertheless contain nicotine. What is increasingly clear is the detrimental effect of nicotine itself on vascular health. It is well established that nicotine increases the heart rate, blood pressure, platelet aggregation and pathological angiogenesis and down-regulation of nitric oxide^{17,18}. Recent studies have shown that nicotine (the addictive component of cigarettes) binds to high affinity nicotinic acetylcholine receptors (nAChRs) cell-surface receptors. This binding has been shown to accelerate the atherogenic process. Unlike free radicals, benzene and tar, nicotine is not thought to initiate plaque formation. However, it accelerates the growth of a pre-existing plaque. This is achieved by vascular smooth muscle cells (VSMC) proliferation, transforming growth factors (TGF) α and β , vascular endothelial growth factors (VEGF) and fibroblast growth factor (FGF) and concomitant suppression of apoptosis^{19,20}. Acute exposure to nicotine alone also worsens endothelial dysfunction in long term smokers²¹.

Further detrimental adverse vascular effects of TC

The complete adverse patho-biological effects of smoking TC are unknown. Aside from containing high amounts of nicotine and the attendant associated effects on plaque formation and atherosclerosis as described above, TC smoking is also known to impair endothelial function^{22,23} because it contains large amounts of harmful oxidants that cause oxidative stress damage to vascular endothelium²⁴, even in passive smokers²⁵ by nitric oxide (NO) uncoupling as well as arginase activation²⁶. Other effects include increasing production and release of endothelin, the up-regulation of matrix metalloproteinases²⁷. Finally, cigarette smoking is also thrombogenic in that it causes changes in platelet membrane fluidity and Na^+/K^+ ATPase activity²⁸ as well as increases platelet aggregation²⁹.

Amato et al³⁰ compared the effect of light versus heavy cigarettes on brachial artery FMD and found no difference in chronic smokers. This suggests that EC may not be the safe alternative that it is being promoted as but as of now, there is no data to suggest that this is true, hence this proposed study.

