2 STUDY OBJECTIVES & OUTCOMES

Table 1: Primary Objectives and Outcome Measures

Primary Objective	Outcome Measure	Timepoints measured
To determine the effect of EC-nicotine free on vascular function as compare to TC.	Change in FMD between the TC group and the EC-nicotine free groups	0 and 4 weeks

Table 2: Secondary Objectives and Outcome Measures

[figure not shown]
Secondary Objectives	Outcome Measures	Timepoints measured
To compare the effects of EC-nicotine vs EC-nicotine free on vascular function.	Change in FMD between EC-nicotine and EC-nicotine free groups	0 and 4 weeks
To compare the effects of EC-nicotine free vs TC on vascular function.	Change in Pulse Wave Velocity between the TC group and the EC-nicotine free groups. Change in Augmentation Index@75bpm between the TC group and the EC-nicotine free groups	0 and 4 weeks
To compare the effects of TC vs EC vs EC nicotine free on oxidative stress.	Change in total F2-Isoprostanes between the TC and EC groups	0 and 4 weeks

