3 STUDY DESIGN

3.1 STUDY DESCRIPTION

VESUVIUS is a single-centre, (Tayside) randomized, 2-cohort parallel group of EC-nicotine and flavouring versus EC-nicotine free and flavouring versus comparator TC arm. These three arms will assess the differential benefits between (1) TC vs EC (2) the presence of nicotine in EC-nicotine versus EC-nicotine free.

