8 STATISTICS AND DATA ANALYSIS

8.1 SAMPLE SIZE CALCULATION

The primary endpoint measurement is change in brachial artery FMD, which is expressed as the maximum FMD percentage change from baseline. Based on our existing data for this measure (mean response 7.8%, SD=3.5%), and assuming mean FMD reductions of 2%, 1% and 0% in the EC-Nicotine-free, EC-Nicotine, and TC groups respectively with a SD of the change in FMD =3.0% (based on our previous study³¹), and a using a sample size calculation using Linear Contrast Tests³⁷ a sample size of 36 subjects in each group will have 80% power to detect an improvement in FMD of 2.0% and 1.0% in the EC-nicotine-free and EC-nicotine groups respectively compared to the TC group at 5% significance. Assuming 10%, 15%, and 20% drop-out rates in the TC, EC-nicotine & EC-nicotine-free groups respectively, we will require 135 completed subjects. **All drop-outs will be replaced to achieve 36 completed subjects in each group.**

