4.1 PRIMARY OUTCOME

 Change in Flow mediated Dilation (FMD) between the TC group and the EC-nicotine and EC-nicotine free groups

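### The hypothesis is about e-cigarettes in general, but the protocol's primary FMD contrast and the 80% power concern only nicotine-free devices, and the SAP names a different primary comparison

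*Protocol*

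**What the plan says.** The hypothesis in the protocol Summary does not distinguish devices by nicotine content: "Endothelial function will be improved on EC compared to TC when measured by flow mediated dilatation (FMD". The aim that follows names both types: "To assess the effects of EC-nicotine and EC-nicotine free on endothelial function as compared to TC". Section 3.1 is equally broad: "These three arms will assess the differential benefits between (1) TC vs EC", with the presence of nicotine listed as a second, separate question.

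The primary outcome is narrower. Table 1 in protocol section 2 gives "Change in FMD between the TC group and the EC-nicotine free groups", and the Outcomes paragraph of the Summary agrees. The only other FMD comparison in Tables 1 and 2 is secondary: "Change in FMD between EC-nicotine and EC-nicotine free groups". Neither table lists EC-nicotine against TC on FMD.

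SAP 4.1 differs. Its primary outcome is the change in FMD "between the TC group and the EC-nicotine and EC-nicotine free groups". SAP 5.1 keeps the protocol's sample size. SAP 8 keeps the linear contrast test and the baseline-adjusted regression on group, and adds the minimisation variables.

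Protocol 8.1 sizes the trial by "assuming mean FMD reductions of 2%, 1% and 0% in the EC-Nicotine-free, EC-Nicotine, and TC groups respectively". The same sentence later speaks of improvement, so I read these as gains. It gives an SD of change of 3.0, 36 per group, 80% power and 5% significance.

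**The concern.** The two arms in the protocol's primary contrast differ in nicotine as well as in tobacco smoke. The protocol does not regard nicotine as incidental; section 1.1 says "What is increasingly clear is the detrimental effect of nicotine itself on vascular health". A difference between these arms could come from removing smoke, removing nicotine, or both, and it gives no direct evidence on devices that still deliver nicotine.

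The Summary motivates the trial by clinicians' inability to recommend EC as a safer substitute. A significant result would satisfy the hypothesis as worded and could be taken as an answer for EC of any kind. On the plan's own assumptions the expected gain with EC-nicotine (1.0) is half that with EC-nicotine free (2.0). Someone following the SAP would meet a second problem: EC-nicotine against TC becomes part of the primary outcome at a sample size that was not derived for it.

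**Working it through.** **Inputs** (protocol 8.1, repeated in SAP 5.1): mean gains in FMD of 0 (TC), 1.0 (EC-nicotine) and 2.0 (EC-nicotine free) percentage points; SD of change 3.0; 36 per group; 5% significance; a linear contrast test.

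**Assumptions**, because the documents do not state them: a two-sided test, and contrast weights of −1, 0, +1 for TC, EC-nicotine and EC-nicotine free. I adopt both because they reproduce the stated figure.

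**1. Reproduce the plan's figure.** For two means, n per group = 2 × (1.96 + 0.842)² × 3.0² / 2.0² = 35.3, so 36. With three groups of 36 (105 degrees of freedom), SE = 3.0 × √(1/36 + 1/36) = 0.707. The noncentrality is 2.0 / 0.707 = 2.83, and power is 80.0%. Alternatives do not match: a one-sided test needs 28 per group, and a two-degree-of-freedom F test across the three arms has 70.4% power at 36.

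**2. Vary the EC-nicotine mean.** The contrast is (−1 × TC mean) + (0 × EC-nicotine mean) + (1 × EC-nicotine free mean).

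| True EC-nicotine gain over TC | Contrast | Power |
|---|---|---|
| +1.0 | 2.0 | 80.0% |
| 0 | 2.0 | 80.0% |
| −1.0 | 2.0 | 80.0% |

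The 1.0 assumed for EC-nicotine does not enter the calculation. For the pairwise comparison in Table 1 this is so by construction.

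**3. EC-nicotine against TC at the assumed 1.0.** The noncentrality is 1.0 / 0.707 = 1.41, and power is 28.9%. The 95% interval would extend about 1.98 × 0.707 = 1.4 points either side of the estimate. For 80% power, n = 2 × (1.96 + 0.842)² × 3.0² / 1.0² = 141.3, so 142 per group. If 45 are recruited per arm and the stated dropout applies, 45 × 0.90 = 40.5 remain in TC and 45 × 0.85 = 38.25 in EC-nicotine, and power is 31.1%.

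**4. What the missing rule in the SAP is worth.** I simulated 200,000 trials at 36 per group with gains of 0, 1.0 and 2.0, testing each EC arm against TC without multiplicity adjustment. Both comparisons succeeded in 27.2%. EC-nicotine alone succeeded in 28.8% and EC-nicotine free in 80.0%, so at least one succeeded in 28.8 + 80.0 − 27.2 = 81.6%. If EC-nicotine has no effect, both succeeded in only 2.4%.

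**5. The existing secondary contrast.** EC-nicotine free against EC-nicotine has 28.9% power at the assumed difference of 1.0. If EC-nicotine has no effect, the difference is 2.0 and power is 80.0%.

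**The case against.** The strongest reply is that the SAP already covers the gap. SAP 4.1 names EC-nicotine against TC in the primary outcome, SAP 5.2 compares all three groups, and the regression in SAP 8 can estimate the comparison if group is fitted as a factor. A reader of the protocol tables alone might infer that the trial never makes this comparison; the documents do not support that. What remains is that the protocol and SAP disagree on what is primary and no rule says what counts as success.

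A second reply is that the feared case would be seen. If nicotine devices gave nothing, the prespecified secondary contrast would have 80.0% power to show it. This also stands, so it would be wrong to say that the trial cannot detect that pattern. But the contrast is secondary. At the planned 1.0 difference it has about 29% power, so a non-significant result would not show that the primary effect carries over to nicotine devices.

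Third, testing the largest expected difference first is legitimate in a trial that the SAP calls explanatory, and Table 1 labels the contrast plainly. I agree; the choice of contrast is not at fault. The general wording of the hypothesis is.

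Two stronger readings should be resisted. One treats EC-nicotine against TC as the pure effect of swapping tobacco for a device, so that half of the primary effect is nicotine removal. Protocol 1.1 says that EC are thought to deliver less nicotine than TC, section 5.5.1 makes the TC arm self-selected, and section 6 sets different smoking instructions before visits for the TC and EC arms. The other reads the hypothesis as a test of both EC arms pooled and reports a power shortfall for it. No document plans such a test.

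**Conclusion.** The point holds in a limited form. The protocol's hypothesis and aim are wider than its primary comparison, the SAP's primary outcome is wider than the protocol's, and the sample size serves only EC-nicotine free against TC. The 80.0% power is the same whether EC-nicotine helps, does nothing or harms, whereas EC-nicotine against TC has 28.9% (31.1% with the expected completers from 45 per arm). A significant primary result would support a statement about nicotine-free devices, subject to the non-randomised TC arm, and not one about EC in general.

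The figures rest on the SD of 3.0, the assumed gains of 2.0 and 1.0, a two-sided 5% test and the inferred weights. They credit no further precision from baseline adjustment, which could raise every power figure. For the protocol's pairwise primary comparison, the independence from the EC-nicotine mean needs none of these values.

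**What to change.** - Make protocol section 2 and SAP 4.1 name the same primary comparison. If both EC arms against TC stay primary, state whether one or both must succeed and give the power under that rule.
- If the primary comparison is EC-nicotine free against TC, restate the hypothesis as: FMD will be improved on nicotine-free EC compared with TC. Limit the primary conclusion to nicotine-free devices, and align the aim and section 3.1.
- List EC-nicotine against TC on FMD as a secondary comparison. Report it with a 95% confidence interval from the planned three-group model, beside the existing EC-nicotine against EC-nicotine free contrast. State that the 80% power does not apply to it (about 29% at 1.0 point).
- Do not describe that comparison as a clean tobacco-to-device effect. Say that nicotine delivery may differ, the TC arm is not randomised, and smoking instructions before visits differ by arm.
- State the contrast weights and the sidedness of the test.

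The cost is wording in the protocol and SAP plus one more reported estimate from a model already planned. It needs no extra participants, visits or measurements. The downside is a narrower headline claim and a less favourable stated power for EC-nicotine.

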1 INTRODUCTION

1.1 BACKGROUND & RATIONALE FOR STUDY

How safe are Electronic Cigarettes?

Electronic cigarettes, also known as e-cigarettes (EC), are increasingly widely used in an attempt to reduce rates of smoking traditional cigarettes (TC). There have been many controversial claims and counter-claims by various experts, social scientists and politicians in the media regarding its effectiveness and safety¹⁻³. The Medicines Health Regulatory Authority (MHRA) has stated that EC are to be licensed and regulated as part of European Union regulations which have imposed tougher restrictions on EC sales and marketing. The MHRA also state that although the amount of harmful carcinogens is only one thousandth of that contained in a TC, that the effects of these toxins, even at much smaller levels are unknown. They are known to be modestly effective in helping smokers to quit, with similar achievement of abstinence as with nicotine patches⁴. In one study, sustained 50% reduction in the number of cig/day at week-24 was shown in 32.5% of participants and sustained smoking abstinence at 24-weeks was observed in 22.5% participants⁵. A recent study looking at using ECs for smoking cessation, published in the Lancet, has concluded that “more research is urgently needed to clearly establish their overall benefits and harms at both individual and population levels⁶. EC are battery-powered devices that simulate tobacco smoking by using a heating element that vaporizes a liquid solution containing a mixture of nicotine and flavourings, while others release a flavoured vapour without nicotine. They are being marketed as a safer alternative to TC.

The benefits of EC on vascular function in terms of the reduction in tar and other contaminants that are present in TC are currently unknown. They are generally thought to deliver smaller quantities of nicotine compared with TC. Furthermore, TC contain >4,000 chemicals, including high levels of nicotine, carbon monoxide, acrolein, and pro-oxidant compounds⁷. However, recent evidence from the United States Food and Drug Administration (FDA) has shown that EC may not be completely harmless and in fact, may contain carcinogens such as nitrosamine and toxic chemicals such as diethylene glycol⁸ which are absent from TC. Subsequent analysis has also revealed the presence of tobacco-specific impurities suspected of being harmful to humans such as anabasine, myosmine, and β -nicotyrine in a majority of the samples tested⁹. Anabasine has been shown to experimentally affect adrenomedullary catecholamine excretion in rats¹⁰. Myosamine causes DNA damage through pyridyloxobutylation similar to the tobacco-specific nitrosamines (TSNA)¹¹. β -nicotyrine is an inactivator of CYP2A6, which is the Cytochrome P450 pathway for nicotine metabolism¹².

The impact of using EC on the cardiovascular system in particular is as yet unknown. The Medicines Health Regulatory Authority (MHRA) has stated that EC are to be licensed and regulated as part of the European Union regulations which have imposed tougher restrictions on EC sales and marketing¹³. The MHRA also state that the amount of harmful carcinogens mentioned in the paragraph above is only one thousandth of that contained in a TC but also concede that the effects of these

toxins, even at much smaller levels are unknown¹⁴. Following this, EC's are banned in health facilities in countries like the Republic of Ireland¹⁵ and parts of Wales¹⁶.

What are the known cardiovascular effects of nicotine?

While EC are sold on the premise that they are a much cleaner alternative to TC in that they do not contain harmful substances like tobacco and tar, they do nevertheless contain nicotine. What is increasingly clear is the detrimental effect of nicotine itself on vascular health. It is well established that nicotine increases the heart rate, blood pressure, platelet aggregation and pathological angiogenesis and down-regulation of nitric oxide^{17,18}. Recent studies have shown that nicotine (the addictive component of cigarettes) binds to high affinity nicotinic acetylcholine receptors (nAChRs) cell-surface receptors. This binding has been shown to accelerate the atherogenic process. Unlike free radicals, benzene and tar, nicotine is not thought to initiate plaque formation. However, it accelerates the growth of a pre-existing plaque. This is achieved by vascular smooth muscle cells (VSMC) proliferation, transforming growth factors (TGF) α and β , vascular endothelial growth factors (VEGF) and fibroblast growth factor (FGF) and concomitant suppression of apoptosis^{19,20}. Acute exposure to nicotine alone also worsens endothelial dysfunction in long term smokers²¹.

Further detrimental adverse vascular effects of TC

The complete adverse patho-biological effects of smoking TC are unknown. Aside from containing high amounts of nicotine and the attendant associated effects on plaque formation and atherosclerosis as described above, TC smoking is also known to impair endothelial function^{22,23} because it contains large amounts of harmful oxidants that cause oxidative stress damage to vascular endothelium²⁴, even in passive smokers²⁵ by nitric oxide (NO) uncoupling as well as arginase activation²⁶. Other effects include increasing production and release of endothelin, the up-regulation of matrix metalloproteinases²⁷. Finally, cigarette smoking is also thrombogenic in that it causes changes in platelet membrane fluidity and Na^+/K^+ ATPase activity²⁸ as well as increases platelet aggregation²⁹.

Amato et al³⁰ compared the effect of light versus heavy cigarettes on brachial artery FMD and found no difference in chronic smokers. This suggests that EC may not be the safe alternative that it is being promoted as but as of now, there is no data to suggest that this is true, hence this proposed study.

There are many ongoing debates on the role of EC and whether or not they are a legitimate replacement for TC. Therefore a clinical trial examining the cardiovascular effects of EC is needed to better inform regulatory authorities and governments regarding the possible cardiovascular risks or benefits of these devices. This proposed study will provide some preliminary useful information on which further definitive studies can later build on.

2 STUDY OBJECTIVES & OUTCOMES

Table 1: Primary Objectives and Outcome Measures

Primary Objective	Outcome Measure	Timepoints measured
To determine the effect of EC-nicotine free on vascular function as compare to TC.	Change in FMD between the TC group and the EC-nicotine free groups	0 and 4 weeks

Table 2: Secondary Objectives and Outcome Measures

[figure not shown]
Secondary Objectives	Outcome Measures	Timepoints measured
To compare the effects of EC-nicotine vs EC-nicotine free on vascular function.	Change in FMD between EC-nicotine and EC-nicotine free groups	0 and 4 weeks
To compare the effects of EC-nicotine free vs TC on vascular function.	Change in Pulse Wave Velocity between the TC group and the EC-nicotine free groups. Change in Augmentation Index@75bpm between the TC group and the EC-nicotine free groups	0 and 4 weeks
To compare the effects of TC vs EC vs EC nicotine free on oxidative stress.	Change in total F2-Isoprostanes between the TC and EC groups	0 and 4 weeks

3 STUDY DESIGN

3.1 STUDY DESCRIPTION

VESUVIUS is a single-centre, (Tayside) randomized, 2-cohort parallel group of EC-nicotine and flavouring versus EC-nicotine free and flavouring versus comparator TC arm. These three arms will assess the differential benefits between (1) TC vs EC (2) the presence of nicotine in EC-nicotine versus EC-nicotine free.

